5.4. Patient Disposition

A detailed description of patient disposition will be provided.

The number and percentage of patients never treated and still under treatment (that is, have not completed the End of Treatment visit) at data cut-off date will be summarized. Patients discontinued from treatment will be presented by reason.

The number and percentage of patients with any important protocol violation will be summarized overall and by type of violation. The predefined important protocol violations are listed below; in addition, any other protocol violations reported from monitoring visits or other sources will be reviewed by the clinical research physician (CRP) and if deemed important will be included in the summary.

- Patient failed to meet study inclusion/exclusion criteria

- Study treatment continued after progressive disease (PD) occurred
- Patient received concurrent prohibited therapy (Listing to identify Anatomical Therapeutic Chemical codes is to be provided for medical review) while receiving study treatment.
- Necitumumab continued after Grade 3 to Grade 4 infusion reaction occurred (as defined by dictionary term “Infusion related reaction”)
- Actual doses of necitumumab were more than 10% greater than protocol defined dose (800 mg), at any of dose administration
- Patient started next cycle less than 18 days later after Day 1 of the most recent treatment cycle
- Patient received more than 2 dose reductions within necitumumab; or for patients starting at abemaciclib 100 mg every 12 hours (Q12H), received 1 or more dose reductions; or for patients starting at abemaciclib 150 mg Q12H, received 2 or more dose reductions; or for patients starting at abemaciclib 200 mg Q12H, received 3 or more dose reductions
- dose-limiting toxicity not reported

5.5. Patient Characteristics

5.5.1. Demographics and Baseline Characteristics

- age (years)
- age group (<65, ≥65 to <70, ≥70 years)
- race (In case of multiple races checked in the case report form [CRF] [for example, “White” and “Asian”], patients will be counted only once in the summary and will be presented as multiple.)
- gender
- ethnicity
- height (cm)
- weight (kg)
- body mass index (BMI)
- Eastern Cooperative Oncology Group (ECOG) performance status

Demographics and baseline characteristics will be summarized.

5.5.2. Disease Characteristics (Pretreatment)

- initial pathological diagnosis basis of determination: histopathological or cytological

- Histology: squamous cell carcinoma of lung, nonsquamous (adenocarcinoma lung + large cell lung cancer), non-small cell lung cancer NOS
- duration of disease (defined as time from diagnosis date to first dose of study drug)
- disease stage

Previous systemic anticancer therapy will be summarized.

5.5.3. Medical History

Preexisting conditions and medical history will be summarized by the number and percentage of patients reporting at least 1 diagnosis and by Medical Dictionary of Regulatory Activities (MedDRA™) preferred term (PT).

5.6. Efficacy Analyses

Efficacy analyses will be performed for the evaluable population. For all time-to-event variables (OS and PFS), the Kaplan-Meier product limit method will be used to estimate the survival curve as well as survival rates at various time points (3-month, 6-month, and 1-year). A 2-sided, 95% confidence interval (CI) for median PFS, median OS, and survival rate at time point will be computed by the Brookmeyer and Crowley method.

5.6.1. Primary Efficacy Endpoint

The primary endpoint for Part B is the PFS rate at 3 months. Progression-free survival rate at 3 months is defined as the rate of PFS at 3 months from the date of first dose of study drug and is determined using the distribution of overall PFS times. The PFS rate at 3 months is estimated using the Kaplan-Meier method.

Progression-free survival is defined as the time from the date of first dose of study drug until first observation of objective (radiographically documented) PD as defined by Response Evaluation Criteria In Solid Tumors Version 1.1 (RECIST 1.1) or death from any cause, whichever comes first. The censoring is taken in the following order:

- If a patient does not have an adequate baseline radiological tumor assessment, then the PFS time will be censored at the date of first study drug, regardless of whether or not objectively determined disease progression or death has been observed for the patient; otherwise,
- If a patient is not known to have died or have objective progression as of the data inclusion cutoff date for the analysis, the PFS time will be censored at the last adequate objective progression-free disease assessment date.

Adequate radiological tumor assessment refers to an assessment with 1 of the following responses: complete response (CR), partial response (PR), stable disease (SD), or PD. If a tumor assessment was done on multiple days, the earliest date for that visit will be used if overall response is PD, and the last date will be used otherwise (censor).

Progression-free survival sensitivity analysis will be performed. The censoring rules for PFS sensitivity analysis are listed in [Table JFCU.5.1](#).

Table JFCU.5.1. Rules for Determining Date of Progression or Censor for PFS Sensitivity Analysis

Situation	Event / Censor	Date of Event or Censor
Tumor progression or death	Event	Earliest date of PD or death
No tumor progression and no death	Censored	Date of last adequate radiological assessment or date of first dose (whichever is later)
unless		
No baseline radiological tumor assessment available	Censored	Date of first dose
No adequate postbaseline radiological tumor assessment available and death reported after 2 scan intervals following first dose	Censored	Date of first dose
New anticancer treatment started and no tumor progression or death within 14 days	Censored	Date of adequate radiological assessment prior to (start of new therapy +14 days) or date of first dose (whichever is later)
Tumor progression or death documented immediately after 2 or more scan intervals following last adequate radiological tumor assessment or first dose (whichever is later)	Censored	Date of last adequate radiological assessment or date of first dose (whichever is later) prior to the missed assessment

Abbreviations: PD = progressive disease; PFS = progression-free survival.

Notes:

- (1) Symptomatic deteriorations (that is, symptomatic progressions, which are not radiologically confirmed) will not be considered as progressions
 - (2) 2 scan intervals = 90 days# for this trial.
- #: 2*(6 weeks+3 days window).

5.6.2. Secondary Efficacy Endpoints

5.6.2.1. Overall Response Rate

The denominator of overall response rate (ORR) includes all evaluable patients and the numerator includes those patients counted in the denominator with a best overall tumor response of PR or CR per RECIST 1.1. Confirmation of objective response is required for this trial. To be assigned a best overall response status of PR or CR, changes in tumor measurements must be confirmed by repeat assessments that should be performed no less than 4 weeks after the criteria for response are first met. In this circumstance, the best overall response can be interpreted as in [Table JFCU.5.2](#). In the case of SD, measurements must have met the SD criteria at least once after first dose at a minimum interval of 6 weeks. Patients' responses after objective progression or start of new anticancer therapy are excluded from the determination of best response. The ORR and its exact 95% CIs will be estimated.

Table JFCU.5.2. Best Overall Response when Confirmation of CR and PR Required

Overall Response First Time point	Overall Response Subsequent Time point	BEST Overall Response
CR	CR	CR
CR	PR	SD, PD, or PR ^a
CR	SD	SD provided minimum criteria for SD duration are met. Otherwise, PD
CR	PD	SD provided minimum criteria for SD duration are met. Otherwise, PD
CR	NE	SD provided minimum criteria for SD duration are met. Otherwise, NE
PR	CR	PR
PR	PR	PR
PR	SD	SD
PR	PD	SD provided minimum criteria for SD duration are met. Otherwise, PD
PR	NE	SD provided minimum criteria for SD duration are met. Otherwise, NE
NE	NE	NE

Abbreviations: CR = complete response; NE = inevaluable; PD = progressive disease; PR = partial response; SD = stable disease.

^a If a CR is truly met at first time point, then any disease seen at a subsequent time point, even disease meeting PR criteria relative to baseline, makes the disease PD at that point (since disease must have reappeared after CR). Best response would depend on whether minimum duration for SD was met. However, sometimes 'CR' may be claimed when subsequent scans suggest small lesions were likely still present and in fact the patient had PR, not CR at the first time point. Under these circumstances, the original CR should be changed to PR and the best response is PR.

5.6.2.2. Disease Control Rate

Disease control rate (DCR) will be analyzed, with the same denominator as defined in ORR. Among patients counted in the denominator, the numerator counts those with a confirmed best tumor response of SD, PR, or CR per RECIST 1.1. The DCR and its exact 95% CI will be estimated.

5.6.2.3. Overall Survival

Overall survival duration is measured from the date of first dose of study drug to the date of death from any cause. For each patient who is not known to have died as of the data-inclusion cut-off date for a particular analysis, OS will be censored for that analysis at the date of last contact prior to the data inclusion cutoff date (contacts considered in the determination of last contact date include adverse event date, lesion assessment date, visit date, and last known alive date).

5.7. Analysis of Safety Data

5.7.1. Extent of Exposure

5.7.1.1. Necitumumab

- number of cycles received by patient
- number of patients treated by cycle
- duration of treatment (in weeks) = $[(\text{Date of last dose} - \text{date of first dose}) + 14] \div 7$
- cumulative dose (mg) = sum of all doses administered
- dose intensity (mg/week) = (cumulative dose) \div (duration of treatment)
- relative dose intensity (%) = dose intensity (mg/week) \div (800 mg *2 / 3 weeks)
- number of dose reductions = total number of reduction steps comparing the planned dose level before each infusion (as entered in the electronic CRF) to the protocol planned dose level as referenced in [Table JFCU.5.3](#).
- dose delay as recorded on the CRF.

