**Test Product, Dosage, and Mode of Administration:**

- Necitumumab is a sterile, preservative-free, intravenous infusion supplied in 50-mL vials containing 16 mg/mL (800 mg/50 mL) of product, and administered at a dose of 800 mg on Days 1 and 8 of each 21-day cycle.
- Abemaciclib is administered orally as capsules (supplied for clinical trial use in strength of 50 mg/capsule) every 12 hours. In Part A, abemaciclib will be administered at increasing doses of 100, 150, or 200 mg Q12H on Days 1 to 21. In Part B, abemaciclib will be administered at a fixed dose determined in Part A of the study Q12H on Days 1 to 21.

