#### 9.3.1. Selection and Timing of Doses

The first treatment will be administered within 7 days of enrollment. Study treatment will be administered as described in Section 9.1.

A cycle is defined as an interval of 21 days.

Administration of necitumumab Day 1 dose will trigger the start of a new cycle. Infusions administered within 3 days before or after the planned infusion time point due to holidays, weekends, bad weather, or other unforeseen circumstances will be permitted and not counted as a protocol deviation. The necitumumab Day 8 dose can be delayed up to 5 days. Beyond that, the Day 8 dose will have to be omitted in order to maintain the 21 day cycle. **A minimum of 7 days' interval between any necitumumab dose must be maintained.**

Abemaciclib will be taken orally every 12 ( $\pm 2$ ) hours on Days 1 through 21 of a 21-day cycle, for a total of 42 doses per cycle. During all cycles, abemaciclib should be taken at approximately the same times each day. If a patient misses or vomits abemaciclib, that dose should be omitted.

In the event of a cycle delay due to logistical reasons (for example, due to patient availability), the patient should continue on abemaciclib treatment. If abemaciclib is interrupted as a result of not having sufficient drug supply, the treatment may be delayed up to 5 days (and not be considered a protocol violation). In exceptional circumstances, a delay  $>5$  days is permitted upon agreement between the investigator and the Lilly CRP.

A patient may continue to receive study treatment until he or she meets 1 or more of the specified reasons for discontinuation (as described in Section 7.3).

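### The fixed 14-day tail in the necitumumab duration formula misstates relative dose intensity when the final Day 8 infusion is omitted or late

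*SAP*

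**What the plan says.** SAP 5.7.1.1 sets necitumumab "duration of treatment (in weeks) = $[(\text{Date of last dose} - \text{date of first dose}) + 14] \div 7". The same 14 days are added whichever infusion came last. Weekly dose intensity is then "dose intensity (mg/week) = (cumulative dose) \div (duration of treatment"), and the relative figure is "relative dose intensity (%) = dose intensity (mg/week) \div (800 mg *2 / 3 weeks"). SAP 5.7.1.2 reports relative dose intensity in bands with cut points at 60, 80, 90, 100 and 110%, including a band for exactly 100%.

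The regimen behind that reference is in the Protocol synopsis: necitumumab is "administered at a dose of 800 mg on Days 1 and 8 of each 21-day cycle". Protocol 9.3.1 supplies the timing rules:

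- "A cycle is defined as an interval of 21 days", and "Administration of necitumumab Day 1 dose will trigger the start of a new cycle".
- Day 8 may slip by as much as 5 days. For a longer slip the rule reads: "Beyond that, the Day 8 dose will have to be omitted in order to maintain the 21 day cycle".
- At least 7 days must separate any two necitumumab doses, so Day 8 can slip later but not earlier.

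The SAP gives no separate duration rule for a patient whose last infusion is a Day 1 dose or a late Day 8 dose.

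**The concern.** Adding 14 days makes sense as a way to carry the patient from Day 8 to the end of a 21-day cycle, and the denominator of 1600 mg per 3 weeks assumes whole 21-day cycles. The Protocol, however, expressly provides for other endings. If the final Day 8 is omitted, the last cycle counts as 14 days, so the missed dose is partly hidden by a shorter duration. If the final Day 8 is late, the last cycle counts as up to 26 days, so a patient who received every dose looks under-dosed.

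At stake is the exposure table for one of the two drugs in the combination. The distortion is largest for short courses. Those matter here: the design's null hypothesis is 50% progression-free at 3 months, and with the SAP's month of 30.4375 days that is 3 × 30.4375 / 21 = 4.3 cycles.

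**Working it through.** **Inputs.** Duration, dose intensity and reference: SAP 5.7.1.1. Bands: SAP 5.7.1.2. Cycle length, Day 8 delay and omission: Protocol 9.3.1. Dose of 800 mg on Days 1 and 8: Protocol synopsis. Let k be the number of necitumumab cycles, with full doses and every earlier infusion on schedule. RDI is relative dose intensity.

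**Step 1. Reproduce the plan's own standard.** The reference is 800 × 2 / 3 = 533.3 mg/week. If the last dose is an on-time Day 8, last minus first is 21(k − 1) + 7 days. Adding 14 gives 21k days, or 3k weeks. The dose is 1600k mg, so the intensity is 1600k / 3k = 533.3 mg/week and RDI is 100% for every k. The formula is right in this case.

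**Step 2. Final Day 8 omitted.** Last minus first is 21(k − 1) days, so the SAP duration is 21k − 7 days, with 2k − 1 doses. Keeping the final cycle at 21 days gives 21k days.

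| k | Dose (mg) | SAP weeks | SAP mg/week | SAP RDI (band) | Cycle-based weeks | Cycle-based mg/week | Cycle-based RDI (band) |
|---|---|---|---|---|---|---|---|
| 1 | 800 | 2 | 400.0 | 75.0% (60 to <80) | 3 | 266.7 | 50.0% (<60) |
| 2 | 2400 | 5 | 480.0 | 90.0% (90 to <100) | 6 | 400.0 | 75.0% (60 to <80) |
| 3 | 4000 | 8 | 500.0 | 93.8% (90 to <100) | 9 | 444.4 | 83.3% (80 to <90) |
| 4 | 5600 | 11 | 509.1 | 95.5% (90 to <100) | 12 | 466.7 | 87.5% (80 to <90) |
| 6 | 8800 | 17 | 517.6 | 97.1% (90 to <100) | 18 | 488.9 | 91.7% (90 to <100) |

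The overstatement factor is 21k / (21k − 7). It depends on duration alone, so it also applies to patients on reduced doses. With full doses, the band is too high for k = 1 to 4 and correct at k = 6.

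**Step 3. Final Day 8 late by d days (1 to 5), all doses given.** The SAP duration is 21k + d days, so RDI = 21k / (21k + d). The cycle-based value is 100%.

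| k | d = 1 | d = 3 | d = 5 |
|---|---|---|---|
| 1 | 21/22 = 95.5% | 21/24 = 87.5% | 21/26 = 80.8% |
| 2 | 42/43 = 97.7% | 42/45 = 93.3% | 42/47 = 89.4% |
| 3 | 63/64 = 98.4% | 63/66 = 95.5% | 63/68 = 92.6% |
| 4 | 84/85 = 98.8% | 84/87 = 96.6% | 84/89 = 94.4% |

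Even one day's delay takes a fully dosed patient out of the exact 100% band.

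**Step 4. Internal consistency.** Take two 2-cycle patients, each given 3 of 4 doses (2400 mg).

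- Cycle 1 Day 8 omitted: (28 + 14) / 7 = 6 weeks, 400 mg/week, 75%.
- Cycle 2 Day 8 omitted: (21 + 14) / 7 = 5 weeks, 480 mg/week, 90%.

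The same dose over the same number of cycles lands two bands apart. The ranking can also reverse: a 2-cycle patient given all 4 doses, the last one 5 days late, shows 89.4%, below the 90.0% of the patient who missed the last dose.

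**Step 5. Check the alternative.** With duration = (Day 1 of the last necitumumab cycle − first dose + 21) / 7, Step 1 still returns 100%, Step 2 returns the cycle-based column, Step 3 returns 100% for every d, and both patients in Step 4 get 75%.

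**The case against.** The strongest reply is that this is an end-of-treatment convention rather than an error. The formula returns exactly 100% for every patient treated as planned, and late Day 1 doses and earlier omissions are already captured by the dates. That is true, and it confines the problem to the final infusion. It does not remove it: Step 4 shows the SAP counting 21 days for every cycle except the last, so the 21-day comparator is the plan's own.

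A reader might infer that intensity is overstated for everyone whose last infusion was a Day 1 dose. The documents do not support that. If treatment stops before Day 8 falls due, no dose was missed, and neither document defines the duration. Counting only 7 days after that final Day 1 would give 150% for 1 cycle or 112.5% for 2, so the SAP's 75% or 90% could equally be called too low.

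A reader might also infer that this is the principal measure of necitumumab delivery, or that the affected patients mostly dropped a dose for toxicity. Neither is stated. SAP 5.7.1.1 also reports cycles, cumulative dose, reductions and delays, and Protocol 12.2.5 and 12.2.9 call for omissions to be summarised, although the necitumumab items listed in the SAP do not name omissions. No frequency of, or reason for, a final Day 8 omission is given. Imaging every 6 weeks, or two cycles, would tend to place stops for scan-detected progression near a cycle end, after Day 8, where the formula works if that dose was given on time.

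**Conclusion.** The point holds for a final Day 8 that is omitted while the 21-day cycle is maintained, and for a final Day 8 that is given late. The overstatement after an omission is 25, 15, 10.4 and 8.0 percentage points for 1, 2, 3 and 4 cycles, with a band change each time, and falls to about 5 points with no band change at 6 cycles. The understatement after a 5-day delay is 19.2 points for 1 cycle and 10.6 for 2.

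These figures assume full 800 mg doses, earlier infusions on schedule, and a 21-day final cycle as the comparator. The number of patients affected cannot be derived from the documents.

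Severity is minor. Relative dose intensity is a descriptive exposure summary; it does not enter the 3-month PFS test, the DLT count or any stated decision rule.

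**What to change.** In SAP 5.7.1.1, replace the necitumumab duration with:

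duration (weeks) = [(Day 1 date of the last cycle in which necitumumab was given − date of first necitumumab dose) + 21] / 7

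Leave the reference of 1600 mg per 3 weeks unchanged. Tie the last cycle to necitumumab explicitly: abemaciclib can continue while necitumumab is interrupted (Protocol 9.3.2.2.2), and counting abemaciclib-only cycles would inflate the necitumumab duration.

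Add one sentence giving the convention for patients who stop before Day 8 falls due. The choice matters: for a 1-cycle patient given one dose, counting 7, 14 or 21 days yields 150%, 75% or 50%. Fix it before the exposure tables are produced.

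The cost is one formula and one sentence in the SAP, and the matching program line. The cycle start is already defined by the Day 1 infusion, so no new data are needed and trial conduct does not change. The downside is that some reported dose intensities become lower.

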5.7.1.2. Abemaciclib

- duration of treatment (in weeks) = $[(\text{date of last dose} - \text{date of first dose}) + 1] \div 7$
- cumulative dose (mg) = sum of all pills (in mg) taken
- dose intensity (mg/week) = (cumulative dose) \div (duration of treatment)
- relative dose intensity (%) = dose intensity (mg/week) \div (7* 2*starting dose (in mg)) where starting dose is 100 mg, 150 mg, or 200 mg according to the patient assignment to the cohorts or Part B
- number of dose reductions = total number of reduction steps comparing the dose entered at the Abemaciclib Dose Adjustment CRF page to the protocol planned dose level as referenced in [Table JFCU.5.3](#).

Table JFCU.5.3. Dose Reductions for Necitumumab and Abemaciclib

Dose Level	Necitumumab	Abemaciclib	Abemaciclib	Abemaciclib
Starting Dose	800 mg	200 mg	150 mg	100 mg
First Dose Reduction	600 mg	150 mg	100 mg	na
Second Dose Reduction	400 mg	100 mg	na	na

Abbreviations: CRF = case report form; na = not applicable.

Note: Actual dose levels entered in the CRF will be rounded to the nearest dose level listed in this table (for example, any necitumumab dose level ≥ 700 mg will be rounded to 800 mg for the purpose of the dose reduction calculation; any necitumumab dose level < 400 mg will be rounded to 400 mg).

The relative dose intensity will be additionally presented categorized (that is, number and percentage of patients with relative dose intensity of <60%, ≥60 to <80%, ≥80 to <90%, ≥90 to <100%, 100%, >100 to <110%, and ≥110%).

Moreover, for necitumumab, the number and percentage of patients with any dose delay, any dose reduction (reduction to first or second dose level) will be presented, along with the reason, as well as the number and percentage of patients with infusion modifications (infusion interrupted); and for abemaciclib, dose adjustments and dose withheld, along with the reason, will be summarized.

Patients who did not receive any amount of a given treatment will be assigned a value of 0 for exposure to that treatment (that is, number of infusions, duration of treatment, cumulative dose, dose intensity, and relative dose intensity).

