### **9.3.2.2. Dose Adjustments and Delays**

#### **9.3.2.2.1. Abemaciclib**

Abemaciclib dose adjustments are allowed both within a cycle and between cycles. Abemaciclib must be reduced sequentially by 1 dose level.

An abemaciclib dose level below 100 mg Q12H is not allowed. For patients starting at abemaciclib 100 mg Q12H, no further dose reduction is permitted. For patients starting at dose level 150 mg Q12H, only 1 dose reduction is allowed.

Abemaciclib may be held up to 14 days to permit sufficient time for recovery from the toxicity. If a dose suspension occurs, the investigator may resume abemaciclib dosing at the same dose level for the remainder of the study or at reduced dose (assuming resolution to at least Grade 1 for nonhematologic and at least Grade 2 for hematologic toxicity). If the patient experiences the same toxicity with the same or greater severity (CTCAE grade) requiring a dose suspension within a cycle or at start of the next cycle, the patient must be dose reduced and not re-challenged a second time at the prior dose level.

If a patient experiences CTCAE Grade 4 hematologic toxicity possibly related to abemaciclib, then dosing must be suspended (until the toxicity resolves to either baseline or at least Grade 2) and the dose of abemaciclib must be reduced as outlined in [Table JFCU.9.2](#).

If a patient experiences CTCAE Grade  $\geq 3$  nonhematologic toxicity possibly related to abemaciclib, then dosing must be suspended (until the toxicity resolves to either baseline or at least Grade 1) and the dose of abemaciclib must be reduced as outlined in [Table JFCU.9.2](#).

If a patient experiences persistent or recurrent Grade 2 nonhematologic toxicity (except diarrhea) possibly related to abemaciclib that does not resolve with maximal supportive measures within 3 days (as outlined in [Section 9.5.3](#)) to either baseline or Grade 1, then dosing should be suspended (until the toxicity resolves to either baseline or at least Grade 1), and the dose of abemaciclib may be reduced as outlined in [Table JFCU.9.2](#).

For patients requiring dose reduction(s), any re-escalation to a prior dose level is permitted only after consultation with the Lilly CRP. After re-escalation, subsequent dose adjustments should be based on the dose of abemaciclib that the patient is currently receiving.

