## **Response Criteria**

### ***Evaluation of Target Lesions***

*Complete Response (CR):* Disappearance of all target lesions. Any pathological lymph nodes (whether target or non-target) must have reduction in short axis to <10 mm. Tumor marker results must have normalized.

*Partial Response (PR):* At least a 30% decrease in the sum of diameter of target lesions, taking as reference the baseline sum diameters.

*Progressive Disease (PD):* At least a 20% increase in the sum of the diameters of target lesions, taking as reference the smallest sum on study (including the baseline sum if that is the smallest). In addition to the relative increase of 20%, the sum must also demonstrate an absolute increase of at least 5 mm. The appearance of 1 or more new lesions is also considered progression.

For equivocal findings of progression (for example, very small and uncertain new lesions; cystic changes or necrosis in existing lesions), treatment may continue until the next scheduled assessment. If at the next scheduled assessment, progression is confirmed, the date of progression should be the earlier date when progression was suspected.

*Stable Disease (SD):* Neither sufficient shrinkage to qualify for PR nor sufficient increase to qualify for PD, taking as reference the smallest sum diameters while on study.

*Not Evaluable:* When an incomplete radiologic assessment of target lesions is performed or there is a change in the method of measurement from baseline that impacts the ability to make a reliable evaluation of response.

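### The SAP's rounding rule hides dose levels below the protocol minimum from its own dose-reduction violation check, and its PD check makes no allowance for continuation that Attachment 6 permits

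*SAP*

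**What the plan says.** **Violation list (SAP 5.4).** Two predefined important violations matter here.

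- Too many dose reductions: more than 2 for necitumumab, and for abemaciclib at least 1, 2 or 3 for patients starting at 100, 150 or 200 mg Q12H. The strictest limb reads "for patients starting at abemaciclib 100 mg every 12 hours (Q12H), received 1 or more dose reductions".
- "Study treatment continued after progressive disease (PD) occurred", with no exception and no statement of which PD date is used.

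**Counting rule (SAP 5.7.1.1 and 5.7.1.2).** The number of reductions is a total of reduction steps relative to the protocol's planned level, with Table JFCU.5.3 as reference. The last row of that table is "Second Dose Reduction 400 mg 100 mg na na" (necitumumab, then abemaciclib starting at 200, 150 and 100 mg). The note below it says "Actual dose levels entered in the CRF will be rounded to the nearest dose level listed in this table". Its examples are "any necitumumab dose level ≥ 700 mg will be rounded to 800 mg for the purpose of the dose reduction calculation" and "any necitumumab dose level < 400 mg will be rounded to 400 mg".

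**Protocol.** Section 9.3.2.2.1 says "An abemaciclib dose level below 100 mg Q12H is not allowed" and permits re-escalation after consultation with the sponsor's physician. Section 9.3.2.2.3 gives 600 mg and then 400 mg as the reduced necitumumab doses. For equivocal progression, Attachment 6 says "treatment may continue until the next scheduled assessment". If PD is then confirmed, its date becomes the earlier date of suspicion.

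**The concern.** A check for excessive reductions should find patients taken below the lowest level the protocol allows. Here the rounding that precedes the count raises exactly those doses to the lowest permitted level, so the step that defines the breach disappears. Nothing else on the predefined list covers low dosing; its only item on dose amount concerns necitumumab given more than 10% above 800 mg.

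The PD item errs the other way. A patient treated through an equivocal scan as Attachment 6 allows, and later confirmed, has dosing after the recorded PD date and fits the wording of the violation.

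At stake is the important-violation summary, which readers use to judge how the trial was conducted. It could miss below-minimum dosing and list patients who followed the protocol.

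**Working it through.** **1. Reproduce the SAP's own rounding examples.** Rounding to the nearest of 800, 600 and 400 mg, with ties upward, gives 700 → 800, 699 → 600, 399 → 400 and 200 → 400. This matches both examples in the note. For abemaciclib, 50 mg rounds to 100 mg, the lowest listed level. A 50 mg Q12H entry is physically possible, because the Synopsis gives a capsule strength of 50 mg.

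**2. Count as levels below the starting dose.** Maximum count = number of listed levels in the column − 1.

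| Column of Table JFCU.5.3 | Listed levels (mg) | Maximum count | SAP 5.4 threshold |
|---|---|---|---|
| Necitumumab 800 | 800, 600, 400 | 3 − 1 = 2 | more than 2, i.e. 3 |
| Abemaciclib 200 | 200, 150, 100 | 3 − 1 = 2 | 3 |
| Abemaciclib 150 | 150, 100 | 2 − 1 = 1 | 2 |
| Abemaciclib 100 | 100 | 1 − 1 = 0 | 1 |

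Every column stops one short of its threshold.

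**3. Same paths with and without rounding.**

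| Path (mg) | Steps, unrounded | Steps, rounded | Threshold |
|---|---|---|---|
| Necitumumab 800→600→400→200 | 3 | 2 | 3 |
| Abemaciclib 200→150→100→50 | 3 | 2 | 3 |
| Abemaciclib 150→100→50 | 2 | 1 | 2 |
| Abemaciclib 100→50 | 1 | 0 | 1 |

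Unrounded, all four are flagged; rounded, none is.

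**4. Count as accumulated downward steps, with re-escalation starting the count anew.** The SAP's phrase about a total of steps allows this reading.

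- Abemaciclib 150→100→150→100: 1 + 1 = 2, which meets the threshold of 2.
- Abemaciclib 200→150→200→150→100: 1 + 1 + 1 = 3, which meets the threshold of 3.
- Necitumumab 800→600→800→600→800→600: 1 + 1 + 1 = 3, which meets the threshold of 3.

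Every dose in these paths is a listed level. The drop below the minimum still adds nothing: after rounding, 400 → 200 and 100 → 50 are each 0 steps.

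**5. Count as a sum over dose records.** Three infusions at 600 mg after a single reduction give 1 + 1 + 1 = 3 and are flagged.

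**6. Patients starting at 100 mg.** The column has one level, so the count is 0 under the readings in steps 2, 4 and 5. The threshold of 1 cannot be met.

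**7. PD flag.** Protocol 10.1.1 schedules scans every 6 weeks (±3 days). From an equivocal scan to the next scheduled one is nominally 6 × 7 = 42 days of permitted dosing. If PD is confirmed and back-dated, all 42 days fall after the recorded PD date.

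**The case against.** The strongest reply is that SAP 5.4 cites neither Table JFCU.5.3 nor its note, which sit under extent of exposure. A reader might infer that the reduction check can never fire. The documents do not support that as a general statement. It needs the levels-below-start reading and the inference that 5.4 uses the 5.7.1 count. On a cumulative reading the check can fire for necitumumab and for abemaciclib starting at 150 or 200 mg. What survives is that 5.7.1 holds the SAP's only definition of the count, and that no reading lets a below-minimum dose add a step.

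Second, the protocol itself limits the number of reductions: one for patients starting abemaciclib at 150 mg (9.3.2.2.1), and discontinuation of necitumumab when more than two are needed (9.3.2.2.3). A cumulative flag might therefore be intended. That is fair, so the re-escalated paths are not shown to be false flags. However, 9.3.2.2.1 also permits re-escalation and bases later adjustments on the current dose, so the SAP must be reconciled with it.

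Third, a reader might infer that the summary will show no below-minimum dosing at all. That goes too far. SAP 5.4 also lets the sponsor's physician add other reported violations judged important, and dose intensity is summarised from doses actually given. These are partial backstops: the first depends on someone reporting the event, and the second does not separate a low dose level from omitted doses.

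Fourth, it is tempting to say that nearly every progressing patient, about half of Part B by 3 months, would be flagged for treatment after PD. The half is the complement of the null rate (1 − 0.50). It includes deaths and progressions after treatment had stopped, and under the research hypothesis the complement is 1 − 0.65 = 35%. The documents give no lag between scan and reading and no frequency of equivocal findings, so no count can be supported.

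**Conclusion.** The point stands in limited form. As written, the reduction count cannot register a dose level below 400 mg necitumumab or 100 mg Q12H abemaciclib, and for patients starting at 100 mg the criterion cannot be met under any of the counting readings examined. On the levels-below-start reading the same is true of every column (2, 2, 1, 0 against 3, 3, 2, 1). On a cumulative reading, in-range sequences can be flagged. All of this assumes that SAP 5.4 uses the count defined in 5.7.1.

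The PD flag would catch compliant patients if it is programmed on the back-dated PD date. The SAP does not say which date applies. The effect is about 6 weeks of permitted dosing per affected patient, with an unknown number of patients.

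The consequence is confined to a descriptive summary. No population in SAP 5.2 excludes patients for violations, and the primary 3-month PFS test is unaffected. Nothing here judges which dose or treatment rule is right.

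**What to change.** 1. Keep the rounding in Table JFCU.5.3 for the exposure summary only.
2. For SAP 5.4, compare the unrounded planned or assigned dose level with the lowest level the protocol lists. Use the planned level before each infusion for necitumumab and the Dose Adjustment page for abemaciclib. Planned level is preferable to amount delivered, because Table JFCU.9.3 requires some infusions to be stopped, and a partly given infusion would otherwise be flagged. State this choice, since 5.7.1.1 refers to planned level and the table note to actual level.
3. State whether a reduction after re-escalation counts again, and reconcile the answer with Protocol 9.3.2.2.1 and 9.3.2.2.3.
4. Base the PD flag on the date PD was documented, and exclude continuation permitted by Attachment 6 after an equivocal finding.

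The cost is SAP wording and the programming of two checks. The dose check uses dose levels that 5.7.1 already takes from the CRF; for the PD flag, confirm that the date PD was documented is available in the data. No dose, treatment rule, population or efficacy analysis changes.
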